Our study period will extend 11 years (January 2004 to December 2014), a period of rapid growth of HDHPs,²² capturing an unprecedented sample size of patients with bipolar disorder transitioning to HDHPs. The intervention cohorts will include individuals who transitioned to HDHPs between January 2005 (after a minimum one year baseline period in a traditional plan) and December 2013 (to allow one year of follow-up). We will follow all subjects for 1 year before and 1 year after the index month of switching (*Figure 3*). Matched controls will be drawn from employers who chose to remain in a traditional plan in the same calendar year, and our matching approach will ensure calendar month of switch is also balanced across the study groups. We will require continuous enrollment for the 24 month study period for both groups.

Figure 3. Study design of HDHP members and controls

* A subgroup of members are “forced switchers” whose employers mandate that they transition from a traditional to a high-deductible health plan

C.5 Study Population for Aims 1-3 [RQ-3; CI-1 to CI-4; HT-1 to HT-4]: Inclusion Criteria: We will include health plan members aged 12 to 64 years at the beginning of the baseline period. Consistent with prior research,⁸⁹⁻⁹¹ we will use medical claims data and a validated algorithm^{36,41,43-45,92,93} to identify members who had at least two ambulatory encounters or one hospital encounter with a diagnosis of bipolar disorder (ICD-9 diagnostic codes: bipolar-I: 296.0, 296.1, 296.4-296.7; bipolar-II: 296.89; and bipolar-other: 301.11 and 301.13^{43-45,89-91}). The first advisory panel committee meeting in October 2015 directly shaped our cohort definition stream of work; advisors agreed that bipolar inclusion criteria should include requiring at least 1 inpatient or 2 outpatient diagnoses, to better ensure that the diagnosis is valid and relevant to the planned analyses. Despite the tightening of our diagnostic criteria, our newest cohort totals remain on target with the estimates in our original power analysis. Eligibility for the study is predicated on the principal diagnosis of bipolar disorder (any diagnosis) not just diagnosis at the first position, as advised by our stakeholder panel. The study cohort was derived through applying the following inclusion rules, therefore defining individuals as eligible for our study:

[name]

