Study cohort: Of 41,638,597 members enrolled in the national insurer during 2004-2012, we found 18,184,556 have a 2-year enrollment span, a study inclusion criterion. Among these, 148,706 have at least 1 inpatient or 2 outpatient diagnoses of bipolar disorder; this reflects a prevalence of 1% members with bipolar disorder, which is consistent with expectation among the commercially insured population. Among 148,706 members with bipolar disorder, 57,028 matched our age criterion (12 to 64 years of age). (We will conduct sensitivity analyses of our main results varying our bipolar diagnosis criteria [e.g., requiring diagnosis prior to index date, requiring only one diagnosis; [CI-5](#)]) To minimize selection bias, our study cohorts will include individuals whose employers offer only a single benefit type with no choice. Our intervention cohorts will include traditional plan members with bipolar illness who experience an employer-mandated switch to HSA-eligible HDHPs with full drug cost-sharing (i.e., out-of-pocket medications payments until the deductible limit is reached), or to HSA-ineligible HDHPs that subject medications only to copayments as in traditional health plans. The control cohort will include members with bipolar illness whose employers offered only a traditional plan for the follow-up year. We estimate that 7,227 have HDHP insurance and 49,801 have traditional plan insurance. **Exclusion Criteria:** We will exclude members age 65 years or older who could be eligible for Medicare benefits, including drug coverage through Medicare Part D. We will also exclude members whose employer offered a choice of health plan. This strengthens our design by reducing potential selection bias due to, for example, healthier members selecting HDHPs or individuals anticipating discretionary utilization. . Input from our panel advisory meetings led to the decision to exclude from our cohort those individuals with a diagnosis of schizoaffective disorder or schizophrenia in order to identify a clinically homogenous group for our study, as advised by our clinical psychiatrist co-investigator [name]. This criterion was further supported by our advisors at DBSA. According to sources at DBSA, schizophrenia and schizoaffective disorder are not comorbidities seen in their peer population. In their judgment, people living with schizophrenia and schizoaffective disorder are unlikely to come to DBSA meetings and would have their needs better met in other settings. The ineligibility criteria therefore included the 3 categories: 1) patients with only 1 outpatient bipolar diagnosis, 2) 1 inpatient or 2 outpatient diagnosis of schizophrenia diagnosis, and 3) 1 inpatient or 2 outpatient diagnosis of schizoaffective disorder. We estimate 3,731 individuals were excluded from the study cohort due to evidence of schizoaffective disorder and schizophrenia. There have been no changes in identifying eligible individuals to enroll in our approved research plan beyond the stakeholder advisory panel decision to exclude schizoaffective disorder and schizophrenia, calculate their overlap with the bipolar population, and exclude them from the final cohort.

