Member-level Covariates include: bipolar disorder type, age, sex, SES, race/ethnicity, state of residence, rurality, Dartmouth Atlas Hospital Referral Region of residence, baseline out-of-pocket and health plan expenditures, number and month (relative to index date) of outpatient/ED/hospital visits, and enrollment in individual versus family coverage. To derive indicators of race/ethnicity, we will first use a variable supplied by the data vendor that applies surname analysis to categorize members as Hispanic or Asian. We will then use US Census block group data¹¹⁶ (geocoding) to indicate predominantly black or white neighborhoods. We will combine both techniques because geocoding is not sensitive in detecting ethnicity¹¹⁷ and surname analysis is non-informative regarding race. **[MD-2]** This validated approach has a high positive predictive value.¹¹⁸⁻¹²² We will have access to individual-level Credit Report-derived variables for income and net worth, which is a major advance over previous studies that used only neighborhood SES measures. We will also determine neighborhood SES (geocoded poverty and education levels) and use principal components approach to calculate a neighborhood SES index.^{99,123,124,125} Adjusted Clinical Groups scores^{94,95} will estimate comorbidity.

[name]

To account for SES variables' data missingness among HDHP and traditional plan adult members, we will use 3 methods to accommodate missingness: (a) multiple imputation, (b) modeling missingness as a member-level characteristic, and (c) excluding members with missing data. If findings differ, we will present results using all 3 methods in manuscripts or attached appendices. We will use SAS procedures PROC MI and PROC MIANALYZE to impute the missing individual level covariates and conduct the statistical analyses under the assumption of missing at random. The SAS procedure PROC MI will impute the missing variables (including individual net worth, income level, poverty level and education level) using other available variables such as age, gender, census block level income, poverty, education and etc. Then we will use PROC MIANALYZE to analyze the imputed data. We will also explore certain Bayesian imputation techniques to handle missing data in case missing is not at random and compare the results.^{146,147}

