(Aim 1) Access to Appropriate Outpatient Care: We will assess changes before and after the index month in the *utilization and adherence* outcomes listed in C.7 for Aim 1 using patient-level *interrupted time series with comparison series*. The interrupted time series design includes multiple observations over time both before and after an intervention (i.e., the plan switch) and adjusts for most threats to internal validity (e.g., secular changes in prescribing, aging of the population) because it adjusts for baseline trends in study outcomes that are unrelated to the intervention.⁸⁰ Furthermore, our strategy of matching on the baseline outcome trend should generate highly robust causal estimates. We will use patient-level segmented linear regression models^{58,84} to statistically estimate patient-level changes in both level and trend in outcomes after the switch to HDHPs, while controlling for autocorrelation of the data and individual-level covariates. The segmented regression models include a constant term; an integer variable indicating *time* in months (t) from the start of the observation period to estimate baseline trend; a binary variable, *intervention*, indicating the period after the index month, to estimate change in level; and an interaction between *intervention* and *time*, to estimate change in trend. We will test the statistical significance of level or trend changes, adjusting for first-order autocorrelation between sequential monthly measurements using the empirical sandwich estimator in GEE.⁵⁸

For selected quality measures (i.e., likelihood of a quarterly outpatient mental health visit or receiving

guideline-recommended lab monitoring when using lithium, valproate, carbamazepine, and 2nd generation antipsychotics; C.7), our approach will be a pre-post with comparison group and difference-in-differences design. Logistic regression models will assess the independent effect of HDHPs on these outcomes, while controlling for patient-level covariates and secular utilization trends (by including index month).^{54,55,99}

(Aim 2) Adverse Patient Clinical Outcomes: To examine the impact of transitioning to HDHPs on changes in rates or risk of psychiatric/non-psychiatric ED visits and hospitalizations, we will use a pre-post with comparison group difference-in-differences design. We will control for patient-level covariates in the models. We will use GLMM to model the effect of HDHPs on annual hospitalization days.

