Differential dropout: Because vulnerable populations such as those with low SES might choose to forego employer health insurance coverage when offered only an HDHP, we will analyze whether differential dropout by group occurred after employer-mandated coverage changes. We will minimize its potential impact on our analyses by performing individual-level propensity matching based on multiple employee-level factors including SES to develop tightly-matched control groups. We will restrict our follow-up duration to 12 months because differential dropout from HDHPs could become more pronounced after the first enrollment year. We expect that we will be able to detect even small changes in utilization soon after the HDHP switch among our very large sample (Section C.10), so that 12 months should be sufficient follow-up to generate policy-relevant insights.

Financial incentives: We will also be unable to track amounts in Health Savings or Health Reimbursement Accounts because these data are only available from employers or financial institutions. This could lead to uncertainty regarding members’ financial incentives or disincentives to seek care. However, the presence of these accounts would bias results toward the null, so that any differences detected are likely to be robust.

Identification of clinical cohort: We will use claims data to identify bipolar disorder. Structured clinical interviews are the gold standard for identifying bipolar illness with high accuracy and inter-rater reliability. Enrollees misdiagnosed as *not having* bipolar disorder (i.e., false negatives) will not be in our cohort and we will be unable to comment on the impact of HDHPs in this group. However, several studies have demonstrated that administrative data can be highly accurate in establishing bipolar disorder for quality assessment, finding that among those identified as having bipolar disorder, 94% are confirmed by chart review.^{66,92,93}

Generalizability: Our inclusion criteria require traditional plan membership for at least a year at baseline, making our results applicable largely to health plan members familiar with the general structure of traditional insurance benefits. This limits generalizability of our results to populations such as previously uninsured low income employees who enter HDHPs. However, given the substantial percentage of employers that are

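### All 12 pre-switch months count as baseline unaffected by the switch, so care moved ahead of the deductible can be read as care lost, and no planned analysis separates the two

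*Combined protocol and SAP*

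**What the plan says.** Section C.4 sets the window: "We will follow all subjects for 1 year before and 1 year after the index month of switching". No month on either side is set aside.

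C.9 (Aim 1) says that the interrupted time series design deals with most threats to internal validity "because it adjusts for baseline trends in study outcomes that are unrelated to the intervention". Its segmented model has a constant, a monthly time variable running "from the start of the observation period to estimate baseline trend", a step "indicating the period after the index month, to estimate change in level", and a trend change. The remaining outcomes use pre-post difference-in-differences over the same two years.

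The plan relies on a matched comparison series. C.9 states that "our strategy of matching on the baseline outcome trend should generate highly robust causal estimates", and the member-level covariates in C.8 include "number and month (relative to index date) of outpatient/ED/hospital visits". C.9 also plans time-series plots.

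Anticipation appears once, in the exclusion criteria of C.5, which guard against "healthier members selecting HDHPs or individuals anticipating discretionary utilization". That concerns who ends up in which plan when the employer offers a choice. The sections on design, matching, outcomes, analysis, power and limitations do not discuss members changing the timing of care before a mandated switch.

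**The concern.** Restricting to single-plan employers deals with choice between plans. It does not stop a member who will be moved to an HDHP from booking a visit or test, or refilling a prescription, while cost-sharing is still low. The plan does not say when members learn of the switch. Its limitations section does expect that some low-SES members "might choose to forego employer health insurance coverage when offered only an HDHP", which implies that members can respond to the offer.

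If care is moved, the late baseline months are too high and the early HDHP months too low. The same contaminated months feed the baseline trend, the pre-year mean and the trend used for matching.

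The direction depends on the outcome:

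- **Visits and laboratory tests:** a fall is exaggerated.
- **Days covered or dose available:** early refills carry over and can hide a fall. This applies mainly to HSA-eligible plans, because C.3 says the other HDHPs generally keep medication copayments. HSA members are 1525 of the 10,800 projected HDHP members in C.10 (14%).
- **Out-of-pocket cost (Aim 3):** services are moved to the cheaper year, so the rise is understated.
- **ED visits and hospitalizations (Aim 2):** probably little affected, since such events are hard to schedule.

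At stake is the main policy reading, namely whether HDHPs reduce care or partly shift its timing.

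**Working it through.** The plan gives no figure for anticipation, so there is nothing of its own to reproduce. The 6% adherence target in C.10 is not a suitable yardstick, because the figures below are for visits and the bias for drug supply runs the other way.

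**Inputs from the plan.** 12 months before and 12 after (C.4); constant, trend, step and trend change (C.9).

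**Assumed, not in the documents.** A flat monthly rate of 1, no true effect, and a share f of one month's visits moved. Months 11 and 12 each gain f/2; months 13 and 14 each lose f/2.

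**Level change.** Least-squares fit of the C.9 model, with the level read at the switch:

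- Spike in months 11-12 alone: -0.276f to -0.311f.
- Dip in months 13-14 alone: -0.311f to -0.276f.
- Both: -0.586f, with trend-change bias zero.

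The paired values are for post-switch time counted from month 12 or from month 13; C.9 does not say which.

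**Role of the controls.** If controls show no spike, the full -0.586f remains. If matching finds controls with the same late rise that then revert, the spike part cancels and the dip part remains: -0.276f to -0.311f, with a trend-change bias of +0.035f per month.

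**12-month count.** The pre mean rises by f/12 and the post mean falls by f/12, so the bias is -f/12 - f/12 = -f/6. With a shared spike only the dip remains, giving -f/12.

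| f | Level, no control spike | Level, shared spike | 12-month count, no spike | 12-month count, shared spike |
|---|---|---|---|---|
| 0.10 | -5.9% | -2.8% to -3.1% | -1.7% | -0.8% |
| 0.25 | -14.7% | -6.9% to -7.8% | -4.2% | -2.1% |
| 0.50 | -29.3% | -13.8% to -15.5% | -8.3% | -4.2% |

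**Length of the window.** Per unit a of monthly spike with an equal dip, the level bias is -0.628a, -1.172a and -1.633a for windows of 1, 2 and 3 months. With a = f/1, f/2 and f/3 this is -0.63f, -0.59f and -0.54f. For a given f, the window length matters little.

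**Effect of month indicators.** With the last two pre-switch months indicated, the spike part goes and the dip part (about -0.3f) stays. With all four months indicated, the bias is zero in this scenario.

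**Precision.** Standard error of the level change, in units of the monthly SD:

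- No autocorrelation: 0.82 with no indicators, 1.00 with two, 1.18 with four. 1.18/0.82 = 1.44.
- Autocorrelation 0.3: 0.94, 1.22 and 1.44. 1.44/0.94 = 1.53.

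**The case against.** The strongest reply is that the premise is not documented. No section gives a notice period or shows that members move care forward, and several passages point the other way: A.6 reports that few new HDHP enrollees knew about their deductible, B.3 mentions confusion over coverage, and C.3 expects many interviewees not to understand their plan. This stands. It means that f may be small and that the point has to be conditional.

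Second, the plan has a comparison series matched on baseline trend and on the month of visits, so a single-series calculation overstates the problem. This stands in part. Matching can roughly halve the bias, but it does so by choosing controls that rose late for some other reason, and it cannot remove the dip after the switch.

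Third, -f/6 is a result for counts. The Aim 1 difference-in-differences outcomes are binary and analysed by logistic regression, and a moved service in Aim 3 is priced differently before and after the switch. This stands; the figure should not be carried over to those outcomes.

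Fourth, patients pay in full until the deductible is met, so a true effect may be concentrated in the first HDHP months, and setting those months aside could discard it. This also stands. It is why the extra analysis should accompany the main one, and why a drop should not have to survive the less precise model before it is believed.

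**Conclusion.** The gap is real but conditional. The plan treats every pre-switch month as unaffected by the switch and has no analysis that tells re-timed care from lost care. If care is moved forward, the level change for visits can be biased by about -0.3f to -0.59f of the monthly rate, and a simple 12-month count by -f/12 to -f/6. The trend-change term is unaffected when controls show no spike. These sizes rest on the assumed share f, a two-month window and an otherwise flat series.

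A reader might infer that anticipation certainly occurs, that the planned estimates are therefore biased, or that a modest shift would by itself account for the adherence change the study is powered to find. The documents do not support these readings. Advance knowledge is implied rather than stated, the size of any shift is unknown, and for drug supply the bias would hide a fall rather than create one.

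**What to change.** Keep the main analysis as written. For the monthly Aim 1 visit and medication outcomes, pre-specify a companion sensitivity analysis in two versions:

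1. Cohort-specific indicators for the last two pre-switch months.
2. The same, plus cohort-specific indicators for the first two HDHP months.

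Where feasible, repeat with matching on the baseline trend, and on month of visits, ended at month -3. State that the two-month window is an assumption, and show the monthly plots beside the results. Report the companion analysis next to the main one, and temper any wording about lost care if they differ. Set no pass/fail rule. In the limitations, give the expected direction of bias by outcome type, including understatement of the rise in out-of-pocket cost.

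The cost is some modelling and re-matching on data already held. With all four indicators the standard error of the level change is about 44-53% larger. The second version may also remove true early deductible effect, while the first leaves the post-switch dip in the estimate, so the two should be read together.

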C.9 Analysis Plan for Aims 1-3 [IR-3; HT-1 to HT-4]: Overview: These analyses will determine how specific outcomes change after employer-mandated switching from traditional plans to HDHPs. To address methodological standard IR-3, we plan to use the most rigorous quasi-experimental retrospective longitudinal designs and analyses available for AIMS 1-3, namely interrupted time series with comparison series matched on multiple baseline covariates as well as the baseline trend of outcome measures. For Aim 4 we will use appropriate standard techniques for qualitative analyses of interview data (detailed below). We will first compare the characteristics of our matched cohorts (HSA-eligible and HSA-ineligible HDHP members, and traditional plan controls) using chi-square tests, t-tests and Poisson or quantile regression.¹²⁶ We will contrast sociodemographic characteristics, employer characteristics, and baseline health care utilization. Subsequent analyses will use time-series plots and rigorous analytical methods appropriate for each outcome, described below. Data collected on the same individuals in successive years are correlated (“repeated observations”). The extended general linear models—generalized estimating equations (GEE) and generalized linear mixed models (GLMM) for binary, count, or continuous measured outcomes—are appropriate methods for estimating parameters to adjust for these correlations within subjects.^{82,83} The term of interest in our GEE or GLMM models will be the interaction between *time* (pre versus post) and *cohort* (HDHP versus traditional plan). Statistical analyses in Aims 1-3 will first compare those transitioning to HDHPs with patients remaining in traditional plans; then contrast effects between HDHP members with full drug cost-sharing (HSA-eligible plans) and those transitioning to HDHPs without full drug cost-sharing (HSA-ineligible HDHPs). Each HDHP group will have as controls only those traditional plan members paired to a given HDHP member during the propensity score match. To examine possible selection effects due to applying our enrollment criteria and propensity matching approaches (see C.10), we will also compare our analytic population to members with bipolar disorder who were excluded from the sample.^[MD-4; CI-2]

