C.10 Sample Size Estimates and Power Calculations [HT-1 to HT-4]: Using 10 years of data (2003-2012), we found 42 million unique adolescents and adults aged 12-64, approximately 450,000 of whom (~1%) had at least one bipolar disorder diagnosis. This is consistent with our expectation of a lower disease prevalence among commercially-insured adults compared with the 3% prevalence estimated by epidemiological surveys,³ because individuals with bipolar disorder less commonly have private insurance.¹³¹ A total of 109,012 of the 450,000 with a bipolar diagnosis met our inclusion criteria of 2 years continuous enrollment, with the first year in a traditional plan, the second in a traditional or HDHP, and no choice from the employer at any point regarding plan type. Projecting to 2014, our sample will include over 10,800 HDHP members (1525 HSA and 9275 non-HSA) and 43,200 matched traditional plan controls with bipolar illness (1:4 matching). Our smallest HDHP subgroups examined for primary outcomes will include 1525 HSA members (smallest medication adherence cohort) and 2160 non-white members (smallest emergency department and hospitalization outcome cohort).

For interrupted time series analyses of medication adherence, based on assumptions including 12 months of follow-up, autocorrelation of less than 0.3, and 0.05 type I error,¹³² we will have greater than 90% power to detect a 6% relative decrease in adherence in our smallest medication outcome subgroup (HSA-HDHP members). For example, we could detect an adherence rate change from 49% (as seen in previous literature¹³³) to 46% with a standard deviation of 1.5%. This is a *smaller* change in adherence than has been observed previously in HDHP-HSA studies.⁵⁷

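### Aim 1 segmented regression: the coefficient labelled as the change in level measures the gap between the fitted lines at month 0, not the step at the switch

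*Combined protocol and SAP*

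**What the plan says.** Section C.9, paragraph on Aim 1, lists the terms of the patient-level segmented model for the utilization and adherence outcomes. "The segmented regression models include a constant term; an integer variable indicating *time* in months (t) from the start of the observation period" carries the baseline trend. Next comes "a binary variable, *intervention*, indicating the period after the index month, to estimate change in level". The last term is the product of these two variables, so the pair is there "to estimate change in level; and an interaction between *intervention* and *time*, to estimate change in trend". The plan then commits to inference on both: "We will test the statistical significance of level or trend changes".

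Section C.4 sets one year of follow-up before and one year after the switch: "We will require continuous enrollment for the 24 month study period for both groups". The switch therefore falls about 12 months after the origin of the time variable.

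The overview of C.9 adds, for the GEE and GLMM models in general, "The term of interest in our GEE or GLMM models will be the interaction between" time and cohort. There, time is a pre/post indicator. That term does not re-centre the monthly variable of the segmented model.

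C.8 to C.10 contain no months-since-switch regressor for this model and no linear combination that recovers the step. The month relative to the index date mentioned in C.8 describes visit covariates, not the regression's time variable.

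**The concern.** In a model with an interaction, the main effect of the post-switch indicator is the difference between the two lines where the other variable equals zero. Here that is the start of observation. The plan labels this coefficient the level change and tests it, but the quantity of interest is the difference at the switch.

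Two things follow if the coefficient is reported under its label. If the trend also changes, the coefficient mixes the step with 12 or 13 months of trend change and can lose its size or reverse its sign. If the trend does not change, the estimate is right on average but imprecise, because it extrapolates the post-switch line back a full year. This model carries the Aim 1 utilization and adherence outcomes, so a wrong level test would affect that aim's main results.

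A related detail is missing. A comparison series is planned, but the listed terms include no cohort term, so the HDHP-versus-control changes in level and trend are not written out.

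**Working it through.** **Inputs.** From the plan: 12 months before and 12 after the switch (C.4); AR(1) autocorrelation below 0.3, type I error 0.05, adherence 49% to 46%, SD 1.5%, power above 90% (C.10). Assumed here: 24 monthly points with the 13th the first post-switch month, a flat baseline, and a two-sided test. The trend changes of 0.1 and 0.25 points per month are illustrative and do not come from the plan.

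**Plan's own figure.** The stated 6% relative decrease is 3/49 = 6.1%. Taking SD 1.5% as the noise of a monthly value, a plain pre/post mean shift in one series has SE 0.612 (autocorrelation 0) to 0.782 (0.3), giving 99.8% to 97% power. That is consistent with the claim of more than 90%. On the same reading, counting from 1, the centred step in the segmented model has SE 1.23 to 1.41 and 68% to 57% power; the coefficient as written has SE 2.54 to 3.17 and 22% to 16%. C.10 does not say which coefficient was powered or what the SD describes, so its figure can be neither confirmed nor refuted. The points below do not depend on it.

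**Algebra.** With E[Y] = b0 + b1·t + b2·I + b3·I·t, the post line minus the extended pre line at month t is b2 + b3·t.
- At t = 0 this is b2, the coefficient the plan labels as the level change.
- At the switch it is b2 + 12·b3 (count from 0) or b2 + 13·b3 (count from 1), which is the step.
- So b2 = step − 12 × (trend change), or step − 13 × (trend change).

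**Noise-free fits of the model as written.**

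| True step | Trend change per month | b2, count from 0 | b2, count from 1 |
|---|---|---|---|
| −3 | 0 | −3 | −3 |
| −3 | −0.10 | −1.8 | −1.7 |
| −3 | −0.25 | 0 | +0.25 |
| −3 | +0.10 | −4.2 | −4.3 |
| −3 | +0.25 | −6 | −6.25 |
| 0 | −0.25 | +3 | +3.25 |

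For example, −3 − 12 × (−0.25) = 0. In every row b2 + 12·b3 (or 13·b3) returned the true step.

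**Precision (GLS, AR(1)).** SE of b2 as written divided by SE of the centred step:

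| Autocorrelation | Count from 0 | Count from 1 |
|---|---|---|
| −0.3 | 1.88 | 2.00 |
| 0 | 1.93 | 2.06 |
| 0.1 | 1.97 | 2.10 |
| 0.2 | 2.02 | 2.16 |
| 0.3 | 2.10 | 2.25 |

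Ordinary least squares with a sandwich variance gives 1.93 to 2.18 for autocorrelation 0 to 0.3. The trend-change SE is identical under both codings, and the recovering contrast has the same SE as the centred coefficient. In an eight-term comparison-series model, the cohort × intervention coefficient has the same ratio, with control SD set at 0.25, 0.5, 1 and 2 times the HDHP SD.

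**Power.** If the centred test has 90% power, its standardized effect is 1.96 + 1.28 = 3.24, and the coefficient as written has power Φ(3.24/ratio − 1.96). For autocorrelation 0 to 0.3 this is 39% to 34% (count from 0) and 35% to 30% (count from 1). At −0.3 it is 41% and 37%.

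**Wrong-sign result.** In a design with 90% power for a 3-point step, a −0.25 per month trend change with no step makes b2 significant in the opposite direction in about 34–40% of studies (autocorrelation 0 to 0.3). With SD 1.5% taken as monthly noise and autocorrelation 0.3, the level test rejects in about 18%.

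**The case against.** The purpose is stated correctly: the plan wants changes in level and trend after the switch. An analyst who keeps to that purpose would use time since the switch or compute the contrast. Harm requires both literal coding and reporting the raw coefficient. The model cites methods sources that may show the intended coding. The fit is sound, the step is recoverable, and the planned time-series plots might expose a reported jump that is not there. All of this is fair as to intent and recoverability. But the sentence defines the time variable explicitly, reuses it by name in the interaction, and attaches the level label to the wrong coefficient. The cited sources are not part of the plan and cannot settle it.

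The illustrative slopes are chosen, and 12 × 0.25 cancels the 3-point step exactly. That stands for the particular numbers. The formula holds for any non-zero trend change.

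The power loss is conditional on a design with 90% power for the step. C.10 ties its figure to the smallest adherence subgroup, 1,525 HSA members. For all 10,800 HDHP members, if the SE scales with 1/√n and 90% is granted at 1,525, then Φ(3.24 × 2.66/ratio − 1.96) is about 97–99% for the same step. So a missed step is a risk for the subgroup and is not shown for the overall comparison. This answers the precision point only; the bias under a trend change does not shrink with sample size.

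The unwritten cohort terms and the C.10 questions are missing detail, not shown errors. That is accepted.

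**Conclusion.** The concern holds. As written, the coefficient that Aim 1 labels and tests as the level change is the difference between the fitted lines at the start of observation. It departs from the step by 12 or 13 times any change in trend. With no trend change it is unbiased, with a standard error 1.9 to 2.2 times too large for autocorrelation 0 to 0.3.

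The direction of the finding follows from the algebra and needs no assumption about SD or sample size. The tabulated values rest on the illustrative slopes and on the switch falling at the 13th of 24 monthly points. The 30–39% power figure rests on a design that has 90% for the step. The fitted lines and the trend-change estimate and test are unaffected. This should be fixed before analysis: the level test answers the wrong question, but the correction is simple and the correct step is available from the same data and model.

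**What to change.** In C.9 (Aim 1), replace the interaction with intervention × (time − switch month), and define the switch month as the first month in which the intervention indicator equals 1. The indicator's coefficient is then the step, and the trend term keeps its meaning. An equivalent alternative is to keep the coding and state that the level change is the contrast b2 + (switch month) × b3, tested with its own standard error.

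In the same edit, write the comparison-series model with cohort, cohort × time, cohort × intervention, and cohort × intervention × (time − switch month). Name the last two as the tested HDHP-versus-control changes in level and trend.

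As a secondary clarification, state in C.10 what the SD of 1.5% describes, which coefficient is powered, whether the calculation is aggregate or patient-level, and whether controls are included. Restate the power figure only if it does not hold for that model.

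The cost is SAP wording and one re-coded variable, with no new data or patients. The power calculation needs rerunning only if it was done for a different model.
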